## 12. DATA REPORTING / REGULATORY CONSIDERATIONS

### 12.1 Protocol amendments

Any amendment to this protocol must be agreed to by the Principal Investigator and reviewed by Celgene. Amendments should only be submitted to IRB/EC after consideration of Celgene review. Written verification of IRB/EC approval will be obtained before any amendment is implemented.

### 12.2 Protocol deviations

When an emergency occurs that requires a deviation from the protocol for a subject, a deviation will be made only for that subject. A decision will be made as soon as possible to determine whether or not the subject (for whom the deviation from protocol was effected) is to continue in the study. The subject's medical records will completely describe the deviation from the protocol and state the reasons for such deviation. In addition, the Investigator will notify the IRB/EC in writing of such deviation from protocol.

Non-emergency minor deviations from the protocol will be permitted with approval of the Principal Investigator.

### **12.3 Data Safety Monitoring Board**

The role of the Data Safety Monitoring Board (DSMB) will be fulfilled by the Weill Cornell Medical College DSMB. The purpose of the Data Safety Monitoring Board (DSMB) is to advise on serious safety considerations, lack of efficacy and any other considerations within the charge to the Committee. Data will be analyzed and submitted to the DSMB annually in order to allow for assessments of response and toxicities.

The DSMB may request additional meetings or safety reports as deemed necessary upon discussion with Celgene and its representatives. The DSMB may stop the study following review of results from each interim analysis. Appropriate efficacy and safety data summaries will be provided to the DMC after each interim analysis.

### **12.4 Data Collection**

The data collection plan for this study is to utilize the HemOnc database to capture all treatment, toxicity, and efficacy data for all enrolled patients.

### **12.5 Regulatory Considerations**

All protocol amendments and consent form modifications will be made by the Principal Investigator. Celgene Corporation will have the opportunity to review and approve the changes prior to submission of these changes to the local IRB and distribution to participating sites.

### **12.6 Investigator responsibilities**

Investigator responsibilities are set out in the ICH guideline for Good Clinical Practice (GCP) and in the US Code of Federal Regulations.

Investigators must enter study data onto CRFs or other data collection system. The Investigator will permit study-related audits by Celgene or its representatives, IRB/EC review, and regulatory inspection(s) (e.g., FDA, EMEA, TPP), providing direct access to the facilities where the study took place, to source documents, to CRFs, and to all other study documents.

The Investigator, or a designated member of the Investigator's staff, must be available at some time during audits to review data and resolve any queries and to allow direct access to the subject's records (e.g., medical records, office charts, hospital charts, and study related charts) for source data verification. The data collection must be completed prior to each visit and be made available to the Celgene representative so that the accuracy and completeness may be checked.

### **12.7 Institutional Review Board/Ethics Committee approval**

The protocol for this study has been designed in accordance with the general ethical principles outlined in the Declaration of Helsinki. The review of this protocol by the IRB/EC and the

performance of all aspects of the study, including the methods used for obtaining informed consent, must also be in accordance with principles enunciated in the declaration, as well as ICH Guidelines, Title 21 of the Code of Federal Regulations (CFR), Part 50 Protection of Human Subjects and Part 56 Institutional Review Boards.

The Investigator will be responsible for preparing documents for submission to the relevant IRB/EC and obtaining written approval for this study. The approval will be obtained prior to the initiation of the study.

The approval for both the protocol and informed consent must specify the date of approval, protocol number and version, or amendment number.

Any amendments to the protocol after receipt of IRB/EC approval must be submitted by the Investigator to the IRB/EC for approval. The Investigator is also responsible for notifying the IRB/EC of any serious deviations from the protocol, or anything else that may involve added risk to subjects.

Any advertisements used to recruit subjects for the study must be reviewed and approved by the IRB/EC prior to use.

#### **12.8 Informed consent**

The Investigator must obtain informed consent of a subject or his/her designee prior to any study related procedures as per GCPs as set forth in the CFR and ICH guidelines.

Documentation that informed consent occurred prior to the subject's entry into the study and the informed consent process should be recorded in the subject's source documents. The original consent form signed and dated by the subject and by the person consenting the subject prior to the subject's entry into the study, must be maintained in the Investigator's study files.

#### **12.9 Subject confidentiality**

Celgene affirms the subject's right to protection against invasion of privacy. In compliance with United States federal regulations, Celgene requires the Investigator to permit Celgene's representatives and, when necessary, representatives of the FDA or other regulatory authorities to review and/or copy any medical records relevant to the study in accordance with local laws.

Should direct access to medical records require a waiver or authorization separate from the subject's statement of informed consent, it is the responsibility of the Investigator to obtain such permission in writing from the appropriate individual.

## 12.10 Study records requirements

The Investigator must ensure that the records and documents pertaining to the conduct of the study and the distribution of the study drug, that is copies of CRFs and source documents (original documents, data, and records [e.g., hospital records; clinical and office charts; laboratory notes; memoranda; subject's diaries or evaluation checklists; SAE reports, pharmacy dispensing records; recorded data from automated instruments; copies or transcriptions certified after verification as being accurate copies; microfiches; photographic negatives, microfilm, or magnetic media; x-rays; subject files; and records kept at the pharmacy, at the laboratories, and at medico-technical departments involved in the clinical study; documents regarding subject treatment and study drug accountability; original signed informed consents, etc.]) be retained by the Investigator for as long as needed to comply with national and international regulations (generally 2 years after discontinuing clinical development or after the last marketing approval). The Investigator agrees to adhere to the document/records retention procedures by signing the protocol.

## 12.11 Premature discontinuation of study

### 12.11.1 Single center

The responsible local clinical Investigator, as well as Celgene, have the right to discontinue this study at any time for reasonable medical or administrative reasons in any single center. Possible reasons for termination of the study could be but are not limited to:

- Unsatisfactory enrollment with respect to quantity or quality.
- Inaccurate or incomplete data collection.
- Falsification of records.
- Failure to adhere to the study protocol.

### 12.11.2 Study as a whole

Celgene reserves the right to terminate this clinical study at any time for reasonable medical or administrative reasons.

Any possible premature discontinuation would be documented adequately with reasons being stated, and information would have to be issued according to local requirements (e.g., IRB/EC, regulatory authorities, etc.).

## 13. STATISTICAL CONSIDERATIONS

### 13.1 Overview

Sample size recommendations for the phase II design are determined according to Simon's two-stage Minimax design [91]. We project an overall response proportion (CR + PR) of 60%, below which the response will be unacceptable, and an overall response proportion of 80% above which the regimen will be considered worthy of further exploration. The null hypothesis that the overall response proportion is less than or equal to 60% will be tested against the alternative hypothesis that the overall response proportion is greater than or equal to 80%. For the purpose of these statistical analyses, responses will be assessed starting after cycle #6 of treatment and then every cycle thereafter.

The sample size computations were performed assuming a 10% level of significance and 80% power. In the first stage, 11 patients will enter the study. If 6 or fewer patients respond, the study will be terminated early and declared to have a negative result. If 7 or more patients respond, enrollment will be extended to 24 patients. At Stage 2, the treatment will be declared effective and worthy of further testing if 18 or more patients respond among the 24 patients entered. This two-stage design yields a  $\geq 0.80$  probability of a positive result if the true percentage of overall responders is  $\geq 80\%$ . It yields a  $\geq 0.90$  probability of a negative result if the true percentage of overall responders is  $\leq 60\%$ .

Table A. Numbers of observed overall responders required to accept or reject  $H_0$  at each stage. Under this design,  $H_0$  will not be rejected at Stage 1

	N	Accept $H_0$	Reject $H_0$
Stage 1	11	$\leq 6$	---
Stage 2	24	$\leq 17$	$\geq 18$

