### **1.3. Primary Endpoint**

- Overall response rate (CR + PR) measured at time of best response

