## 5.2 Investigational Study Drug Combination (THRIL)

### **Starting with Cycle 1:**

#### **A cycle is 28 days:**

Thalidomide 50 mg every ODD day, days 1-28 every 28 days

Lenalidomide every EVEN day, days 1-28 every 28 days at the dose indicated above and with possible dose escalation as described in 5.1.

Rituximab 375 mg/m^2 IV on days 1, 8, 15 and 22 (+/- 2 days) starting with Cycle 1 and then again on the same weekly x 4 schedule every 6th cycle through Cycle 19 (Cycles 7, 13, and 19).

Responses will be assessed at monthly intervals using the response criteria outlined by the IWCLL update of the 1996 NCI-Working Group criteria. Patients will remain on treatment until they demonstrate disease progression or unacceptable toxicity. It will be important for the investigator to differentiate disease progression from tumor flare. While no strict criteria can be established for this distinction, rapid changes in clinical status that occur within four weeks of a dose escalation are likely to be tumor flares and should be treated as such.

Tumor flare has been described with both thalidomide and lenalidomide treatment. Therefore, patients should be monitor closely for signs and symptoms of tumor flare for four weeks after each increase in dose. Prophylaxis for (TFR) is not recommended. Grade 1 TFR may be treated with NSAIDs (i.e. ibuprofen 400-600 mg orally every 4-6 hours as needed). TFR  $\geq$  Grade 2 may be treated with corticosteroids. Narcotic analgesics may be added as needed for pain control in subjects experiencing  $\geq$  Grade 2 tumor flare. If corticosteroids are used, the following dosage schedule is

recommended: prednisone 20 mg PO QD x 7 days followed by 10 mg PO QD x 7 days. (See Appendix D: Cairo Bishop Tumor Lysis Definition and Grading Criteria.)

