### 5.4 Drug Administration

#### 5.4.1 Dosing regimen

- Cycle -1: patients will receive thalidomide 50 mg PO daily on days 1-14 or lenalidomide PO on days 1-14, followed by no treatment days 15-28, as described previously in 5.1.
- Cycle 1 and subsequent cycles: Patients will receive thalidomide 50 mg (every **ODD** day on days 1-28 of a 28 day cycle) with lenalidomide (every **EVEN** day on days 1-28 of a 28 day cycle), as described previously. Each cycle will be 28 days in length.
- Cycle 1: Patients will also receive rituximab 375 mg/m^2 IV on Days 1, 8, 15 and 22 and then again on the same weekly x 4 schedule every 6th cycle through Cycle 19 (Cycle 7, 13, and 19), as described previously.

Patients unable to tolerate either thalidomide or lenalidomide will be removed from protocol. Patients unable to tolerate rituximab can continue on with protocol treatment without additional rituximab being administered.

Dosing of thalidomide and lenalidomide should be at bedtime in order to allow for the sedative effects of thalidomide to not cause daytime somnolence and to maintain regular dosing intervals. **Only enough lenalidomide for one cycle of therapy will be supplied to the patient each cycle.** At the start of any non-clinic visit treatment cycles subsequent to Cycle 24, one cycle of study drug will be shipped to the subject.

See Section 5.5 for allopurinol and oral hydration requirements as prophylaxis against tumor lysis syndrome (TLS).

Thalidomide and lenalidomide capsules should be swallowed whole, and should not be broken, chewed or opened.

If a dose of thalidomide or lenalidomide is missed, it should be taken as soon as possible on the same day. If it is missed for the entire day, it should not be made up.

Patients who take more than the prescribed dose of thalidomide or lenalidomide should be instructed to seek emergency medical care if needed and contact study staff immediately.

Subjects experiencing adverse events may need study treatment modifications (See section 5.6).

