11.4 **Stable disease:** patients who have not achieved a CR or a PR, and who have not exhibited progressive disease, will be considered to have stable disease.

11.5 **Relapse:** patients who has previously achieved a CR or PR, but after a period of 6 or more months, demonstrate evidence of disease progression.

11.6 **Refractory disease:** disease progression within 6 months of the last treatment.

11.7 **Duration of response definitions:**

1. **Duration of response:** from the end of the last treatment until evidence of progressive disease.
2. **Time to response:** interval from the first treatment day to the date response first identified.
2. **Progression-free survival:** interval between the first treatment day and the first sign of disease progression.
3. **Event-free survival:** interval between the first treatment day to the first sign of disease progression, treatment for relapse, or death, whichever occurs first.
4. **Survival duration:** interval between the first day of treatment and death

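### The two-stage test counts responses only after Cycle 6, but the primary endpoint is best response with no earliest time, so an early leaver with a documented response has no settled classification.

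*Combined protocol and SAP*

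**What the plan says.** - **Endpoint.** Section 1.3 (and the Schema): "Overall response rate (CR + PR) measured at time of best response". No earliest assessment is named.
- **Analysis window.** Section 13.1: "For the purpose of these statistical analyses, responses will be assessed starting after cycle #6 of treatment and then every cycle thereafter". Section 13.5.1 repeats the window for the interim analysis.
- **Data collection.** Section 5.2: "Responses will be assessed at monthly intervals using the response criteria outlined by the IWCLL update". Section 11 gives a four-week interval. The Section 10 calendar marks a response assessment on Day 1 of Cycles 3 to 6, and a response assessment with CT at discontinuation from therapy.
- **CT timing.** Section 11 requires CT for both CR and PR. The calendar shows CT at screening, at Cycle 7 Day 1 and at discontinuation. Footnote 12 makes routine CT six-monthly and adds a CT within four weeks when blood counts reach CR level.
- **Early exit.** Section 5.4.1: "Patients unable to tolerate either thalidomide or lenalidomide will be removed from protocol". Section 5.6 ends treatment if either oral drug is stopped for any reason.
- **Decision rule.** Section 13.1 stops at stage 1 with 6 or fewer responders in 11, and declares success with 18 or more among the 24 patients entered. Sections 13.2 to 13.4 define a safety population, but no efficacy-evaluable population and no replacement rule.

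**The concern.** The counts of 7/11 and 18/24 decide the trial, and two stated rules feed them. Under Section 1.3, a CR or PR documented in Cycle 4 is a best response. Under Sections 13.1 and 13.5.1, an assessment in Cycle 4 lies outside the window. For a patient still in response after Cycle 6 the rules agree. They disagree for a patient who stops an oral drug, or loses response, before the first counted assessment.

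Such a patient can arise. Someone removed for intolerance in Cycle 4 has a discontinuation CT and response assessment that may show PR. Someone whose blood counts reached CR level early may have a confirming CT and then lose the response. Two analysts following the text could report different primary counts. A third count is possible if the patient is treated as non-evaluable and dropped from the denominator.

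**Working it through.** **1. Reproduce the design.** Inputs, all from Section 13.1: null "We project an overall response proportion (CR + PR) of 60%, below which the response will be unacceptable"; alternative "an overall response proportion of 80% above which the regimen will be considered worthy of further exploration"; error rates "assuming a 10% level of significance and 80% power"; n1 = 11, continue if 7 or more respond; n = 24, success if 18 or more respond.

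P(success | p) = sum over x = 7 to 11 of P[Bin(11, p) = x] × P[Bin(13, p) ≥ 18 − x].

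| Stage 1 responders x | Needed in the next 13 | Term at p = 0.80 | Term at p = 0.60 |
|---|---|---|---|
| 7 | 11 | 0.1107 × 0.5017 = 0.0555 | 0.2365 × 0.0579 = 0.0137 |
| 8 | 10 | 0.2215 × 0.7473 = 0.1655 | 0.1774 × 0.1686 = 0.0299 |
| 9 | 9 | 0.2953 × 0.9009 = 0.2660 | 0.0887 × 0.3530 = 0.0313 |
| 10 | 8 | 0.2362 × 0.9700 = 0.2291 | 0.0266 × 0.5744 = 0.0153 |
| 11 | 7 | 0.0859 × 0.9930 = 0.0853 | 0.0036 × 0.7712 = 0.0028 |
| Total | | 0.8015 | 0.0930 |

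(Totals are from unrounded terms.) An exhaustive search returns the same minimax design, 6/11 and 17/24. The design arithmetic is sound. The open question is which responses enter the counts.

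**2. Case A: 60% and 80% are best-response rates, but only post-Cycle-6 responses are counted among all patients entered.** Let f be the share of responders whose only documented response precedes the window. The documents give no value, so f is assumed. The countable rate at a true 80% is 0.80 × (1 − f).

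| f (assumed) | Expected responders lost, 24 × 0.80 × f | Countable rate | P(success) |
|---|---|---|---|
| 0 | 0 | 0.80 | 0.8015 |
| 2.5% | 0.48 | 0.78 | 0.7252 |
| 5% | 0.96 | 0.76 | 0.6406 |
| 10% | 1.92 | 0.72 | 0.4638 |

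An expected loss of exactly one responder gives a rate of (19.2 − 1)/24 = 0.758 and power 0.633.

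**3. Case B: 60% and 80% already refer to the after-Cycle-6 rule.** If that rule is applied, nothing changes: 0.0930 and 0.8015. If best response is counted instead, early-only responders add d points to a regimen whose after-Cycle-6 rate is 60%.

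| d (assumed) | Rate entering the count | P(success) |
|---|---|---|
| 0 | 0.600 | 0.0930 |
| 2.5 points | 0.625 | 0.1411 |
| 5 points | 0.650 | 0.2048 |
| 10 points | 0.700 | 0.3796 |

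**4. How many patients could be affected?** CR and PR need CT. From first dose until Cycle 7, the only scheduled sources are the CT triggered by CR-level blood counts and the discontinuation CT. A patient changes class only by having one of these show CR or PR and then having no response at any counted assessment. That points to small f and d, but the documents do not bound either.

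**The case against.** The strongest reply is that there is no contradiction. Section 1.3 names the measure, Section 13.1 supplies its window, and a specific analysis rule normally governs a general label. A late window also fits the regimen: with 5 mg steps from Cycle 2, a patient starting at 5 mg reaches the 25 mg maximum in Cycle 5 at the earliest. The 60% and 80% stand in the same paragraph as the window, so they may well be after-Cycle-6 rates, in which case power is untouched.

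Much of this stands. It is why no single power loss can be asserted, and why the design itself should not be called wrong. What it leaves open is the classification. If Section 13.1 sets a landmark, the endpoint is no longer best response and Section 1.3 should say so. On either reading, no text places the early leaver among the 24. That such a patient is a failure is an inference from the denominator, not a stated rule. One could also take 13.1 as only fixing when response data are first reviewed, but it does not say that.

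A reader might also infer that the window puts a floor of about Cycle 7 under time to response. The documents do not support this. Section 11.7 defines that endpoint as "interval from the first treatment day to the date response first identified", with no cycle limit, and the window sentence sits with the hypothesis test. For patients who stay on treatment, most of the delay in documenting a response comes from the CT calendar, which rewording 13.1 would not alter.

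**Conclusion.** The point holds as a gap in the primary decision rule: the response window is not aligned between Section 1.3 and Sections 13.1 and 13.5.1, and early leavers with a documented response are unclassified. Probably few patients are affected, but one is enough to move 18/24 to 17/24, or 7/11 to 6/11.

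The size depends on two things the documents do not give: the share of early-only responders, and which definition the 60% and 80% describe. In Case A, power at a true 80% runs from 0.80 with no loss to 0.46 with 10% loss. In Case B, power stays 0.80 if the window is applied, and counting best response instead puts the false-positive chance at 0.14 to 0.38 for 2.5 to 10 added points. These are conditional ranges, not estimates of what will happen. With one definition used throughout, and both thresholds referring to it, the design stands unchanged.

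**What to change.** Use one response window in Sections 1.3, 13.1 and 13.5.1.

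- **To match the stated endpoint:** count as a responder any patient meeting the Section 11 criteria for CR or PR at any on-study assessment, including the CR-triggered and discontinuation CTs. Class patients with none as non-responders among the 24 (and among the 11 at stage 1). Confirm that 60% and 80% refer to this definition; if they do not, restate them and recheck the design.
- **If a post-Cycle-6 landmark is intended:** restate Section 1.3 accordingly, and say that patients who leave before the first counted assessment are non-responders. Section 13.5.1 times the first look for when eleven patients reach cycle four, so the last of them would have no countable response yet; the stage 1 count would need its own timing.

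Settle the choice without reference to the response counts. The cost is wording plus the check on the two thresholds. Every assessment needed is already on the calendar, and no added patients or visits follow unless the thresholds have to change.

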### 13.2 Datasets to be analyzed

Primary Endpoint:

- Overall response rate (CR + PR)

Secondary Clinical Endpoints:

- Progression Free Survival
- Duration of response
- Time to response
- Overall survival
- Toxicity profile

### 13.3 Statistical Methodology

Primary Endpoint:

- The primary endpoint of response rate (overall, CR, PR) will be estimated and a 95% confidence interval will be estimated via binomial proportions

Secondary Endpoints:

- With adequate follow-up time, progression-free survival (PFS) will be assessed by Kaplan-Meier survival analysis and 95% confidence intervals will be calculated using Greenwood's formulae. PFS will be defined as the time from the first treatment day until objective or symptomatic progression (or until date of last follow-up if no progression).
- Duration of Response: from the end of the last treatment until evidence of progressive disease.
- Time to Response
- Overall Survival
- The frequency of subjects experiencing toxicities will be tabulated. Toxicities will be assessed and graded according to CTCAE v4.0 terminology. Exact 95% confidence intervals around the toxicity proportions will be calculated to assess the precision of the obtained estimates.

